6.2 Analysis of Binary Endpoints

The set of binary endpoints to which this section pertains are given as follows:

1. Incidence of 30-day all cause readmissions

- 2. Incidence of 90-day all cause readmissions
- 3. Use of TCM billing codes

For the analysis of 30- and 90-day all cause readmissions, patients who have continuous coverage over the 30- or 90-day reference period will be included in the analysis. For analysis of TCM billing codes, patients who have continuous coverage over the 30-day period following discharge from the index hospitalization will be included in the analysis. The percentage of patients with incomplete coverage over the 90-day period following discharge from the index hospitalization is expected to be low. In the event that more than 10% of the patients linked to claims data have incomplete coverage over the relevant 30- or 90-day reference period, we will assess the robustness of any important findings to exclusion of these patients from analyses using techniques such as multiple imputation from a time-to-event model that accounts for the observed follow-up period for patients who drop out of coverages during the relevant reference period.

For readmission endpoints, patients who die prior to the end of the reference period without a qualifying readmission will be treated as not having a readmission. Prior analyses of 90-day mortality based on the full COMPASS cohort has demonstrated that the percentage of patients who die within 90 days of discharge from the index hospitalization is approximately 2.0% and did not differ by treatment arm.⁴ Thus, the impact of excluding patients who did not survive for the entire reference period is not expected to strongly influence results. Nonetheless, in the event that more than 5% of the patients linked to claims data die within the reference period, we will assess the robustness of any important findings by performing a sensitivity analyses that includes these patients as having met the endpoint for all cause readmissions.

For all binary endpoints, we will employ generalized linear mixed models (GLMM) with a logistic link function. Models will include a hospital-specific random effect, and adjust for the covariates described in Section 6.1.

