Тур	e: 🗆 Home 🗆 Mobile 🗆 Work	□ Other	
c. Alternate Mailir	ng Address		
	Address Line 1		
	Address Line O		
	Address Line 2		
	City	State	Zip
15. Relationship to p	patient?		
	 □ Spouse (husband or wife) □ Sibling □ Son or daughter □ Friend or neighbor □ Parent or legal guardian □ Other, specify: 		
D DEMOCRAPHIC	S AND IN-HOSPITAL DATA		

☐ Asian☐ American☐ Native HI): rican American Indian / Alaska Native / Other Pacific Islander	
18. Hispanic ethnicity: ☐ Yes	□ No	
☐ Medicare	Supplemental Insurance / Med surance npus / other	ligap
20. Does the patient have documented	ed past medical history of the f	ollowing (check all that apply):
☐ Stroke☐ Transient ischemic attack	☐ Hypertension☐ Dyslipidemia	☐ Chronic renal insufficiency☐ Heart Valve☐ Current pregnancy or within 6
 □ Atrial Fibrillation or Flutter □ Myocardial infarction or CAD □ Congestive heart failure □ Carotid stenosis □ Peripheral arterial disease 	 ☐ Smoking ☐ Depression ☐ Drug/alcohol abuse ☐ Family history of stroke ☐ Migraines 	weeks post-partum Hormone replacement therapy Sickle cell Sleep apnea Diabetes mellitus
21. Please enter the body mass inde	x (BMI) kg/m²	□ Not documented
22. What was the patient's ambulator	ry status prior to admission ?	
		vithout a device)
23. Initial NIH Stroke Scale Score (00)-42)	Not documented
25. Did the initial exam show aphasia	a? ☐ Yes ☐ No / not do	ocumented
26. Hospital admission date for this e	event: / /	/
☐ No admission date; patient was	not admitted as an inpatient (s	select reason below)
	lirectly from ED to home rom observation status without	inpatient admission

2/a. If YES	S, check all that apply:	
☐ Hom	e health Physical Therapy e health Occupational Therapy e health Speech Therapy Outpatient Physical Therapy Outpatient Occupational Therapy Outpatient Speech Therapy	
27b. If NO	indicate why not	
☐ Patie	nt not evaluated for need of rehab services nt not in need of rehab services nt / family refused r reason	
28. What w	as the patient's ambulatory status at discharge?	
	 □ Able to ambulate independently (with or without a device) □ With assistance (from person) □ Unable to ambulate □ Not documented 	
30. Hospita	I discharge date:	
	ollow-up clinic visit with a nurse, nurse practitioner, or physician assistant (i.e. p nal care clinic, neurologist, or other doctor visit) scheduled prior to discharge?	rimary care,
	☐ Yes → Fill in type and date below	
31a	☐ No If YES, check all visit types that apply and enter the date (if known)	

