4.5 Transitional Care Management Billing

According to CMS guidelines,³ transitional care management (TCM) requires four core components: (1) transition in care from an inpatient setting to a community setting; (2) receipt of communication from a provider (direct contact, telephone, or electronic) within 2 business days of discharge; (3) moderate or high complexity medical decision making; and (4) a face-to-face clinical visit within 7 or 14 calendar days of discharge from the inpatient setting.

The TCM billing endpoint will be defined as incidence of TCM billing with the associated estimand being the odds ratio from a logistic model. Transitional care management billing is defined as an office visit billing through Current Procedural Terminology (CPT) codes 99495 (for a visit within 14 days of index hospitalization discharge) and 99496 (for a visit within 7 days of index hospitalization discharge). Because TCM billing codes became effective under Medicare's Physician Fee Schedule, and BCBS and Medicaid may not consistently use these codes, this endpoint will be defined for FFS Medicare participants only. The 30-day TCM eligibility period begins on the beneficiary's inpatient discharge date and continues for the next 29 days. Medicare beneficiaries who die or who have a hospital readmission within 30 days following the index discharge are not eligible to have a TCM claim. Therefore, even if they received TCM core components, such patients do not meet the TCM billing criteria. Because TCM billing can be rendered by physicians and non-physician practitioners in inpatient and outpatient setting, our assessment of TCM code billing will include claims from all practitioners.

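### The TCM billing denominator in SAP 6.2 has no inpatient condition, so patients sent home directly from the ED, ineligible under SAP 4.5, enter it and would normally count as non-events

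*SAP*

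**What the plan says.** SAP 4.5 (Transitional Care Management Billing) lists four required components of TCM. The first is "1) transition in care from an inpatient setting to a community setting". The clock is tied to the same event: "The 30-day TCM eligibility period begins on the beneficiary's inpatient discharge date". The endpoint is binary: "The TCM billing endpoint will be defined as incidence of TCM billing with the associated estimand being the odds ratio from a logistic model". The event is a billed CPT code, 99495 or 99496, from any practitioner. On payer, "this endpoint will be defined for FFS Medicare participants only". Section 4.5 also says that beneficiaries who die or are readmitted within 30 days "are not eligible to have a TCM claim".

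SAP 6.2 (Analysis of Binary Endpoints) gives the inclusion rule: "For analysis of TCM billing codes, patients who have continuous coverage over the 30-day period following discharge from the index hospitalization will be included". SAP 5.1 limits the FFS Medicare population by type of coverage only (Parts A and B, no Part C). Neither section asks for an inpatient index stay.

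The Protocol's inclusion criterion is discharge home from a participating hospital with stroke or TIA, and inpatient admission is not required. Item 26 of the Phase 2 enrolment form (Appendix 38) has a box beginning "No admission date; patient" for people not admitted as inpatients. Its listed reasons include going home directly from the ED and being discharged from observation without an inpatient admission. The Phase 1 enrolment form has the same box, but its list of reasons is only partly legible in the text available.

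**The concern.** Section 4.5 recognises that some patients fall outside TCM by rule, and it restricts the payer because other insurers may not use the codes consistently. Section 6.2 does not carry that logic into the denominator for patients who were never admitted. Take a TIA patient with FFS Medicare who goes home from the ED and attends the COMPASS clinic on day 10. By the SAP's own criterion there was no inpatient-to-community transition, so normally no TCM code would be billed. The patient received the intended visit and still counts as not billed.

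Use of TCM codes is a named secondary outcome, compared between arms in Phase 1 and between phases in Phase 2. Whether a patient with TIA or minor stroke is admitted depends partly on hospital practice. With about 20 randomised units per arm, the ineligible share can differ between arms by chance, and it can drift between phases. The odds ratio would then move with no change in TCM delivery.

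**Working it through.** The documents give no sample size, effect or rate for TCM billing, so there is no figure of the plan's to reproduce. The check has two parts.

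**1. Does any provision remove these patients?**

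| Place | Condition applied | Removes ED-to-home patients? |
|---|---|---|
| Protocol inclusion criteria | Discharged home with stroke or TIA | No |
| SAP 5.1 | FFS Medicare Parts A and B at index discharge | No |
| SAP 6.2 | 30 days of continuous coverage | No |
| SAP 4.5 | Death or readmission within 30 days named as ineligible | Not mentioned |
| SAP 6.1 and 6.1.1 | Covariate lists | Admission status is in neither |

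**2. What could it do to the odds ratio?** Every input here is an assumption. Let p be the billing rate among eligible patients and q the ineligible share of the denominator. If ineligible patients are never billed, the observed rate is p(1 − q), and

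OR = odds[p_I(1 − q_I)] / odds[p_U(1 − q_U)], where odds(x) = x/(1 − x), I = intervention and U = usual care.

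*Equal shares in both arms:*

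| p_U, p_I | q = 0 | q = 10% | q = 20% | q = 30% |
|---|---|---|---|---|
| 10%, 30% | 3.86 | 3.74 | 3.63 | 3.53 |
| 20%, 40% | 2.67 | 2.56 | 2.47 | 2.39 |
| 30%, 60% | 3.50 | 3.17 | 2.92 | 2.72 |

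Example, first row at q = 30%: the observed rates are 0.30 × 0.70 = 0.21 and 0.10 × 0.70 = 0.07, so OR = (0.21/0.79)/(0.07/0.93) = 3.53. Against 3.86 that is a fall of about 8%. The bottom row falls by about 22% (2.72 against 3.50), because the attenuation grows with the billing rate. Both observed rates fall by the factor 1 − q in every case.

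*Unequal shares, p_I = 30%, p_U = 10% (OR among eligible patients 3.86):*

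- q_I = 15%, q_U = 25%: rates 0.255 and 0.075, OR 4.22 (+9%).
- q_I = 25%, q_U = 15%: rates 0.225 and 0.085, OR 3.13 (−19%).

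*Unequal shares with no true effect, p = 20% in both arms:*

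- q_I = 10%, q_U = 20%: rates 0.18 and 0.16, OR 1.15. Reversed: 0.87.
- q_I = 5%, q_U = 25%: rates 0.19 and 0.15, OR 1.33. Reversed: 0.75.

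**The case against.** The strongest reply is that the SAP never says ED or observation patients are kept. Section 6.2 counts from discharge after the index hospitalization, which could be read as inpatient only, and the Phase 1 SAP, to which this document is an addendum, may define the term. That Phase 1 SAP is not among the documents reviewed. Within this SAP, however, the term is used for the whole cohort, including when 6.2 cites 90-day mortality in all COMPASS patients. At best the wording is ambiguous, and it needs settling.

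Three further points stand in part.

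- **Estimand.** Billing among all covered FFS patients is a legitimate pragmatic estimand, and the Protocol's aim is simply use of the codes. Index status is set before post-discharge care but after hospitals were randomised, at hospitals that know their arm. Conditioning on it could introduce selection. This is a reason to keep the all-covered analysis beside the eligible-set analysis.
- **Adjustment.** Stroke versus TIA and NIHSS are in the model and may absorb part of an imbalance. They are proxies. A hospital random effect does not remove a difference in ineligible share between arms.
- **Observation stays.** A reader might infer that these patients are ineligible too. The documents do not settle that. SAP 4.1 names inpatient and observation as separate statuses, but 4.1 and 4.6 count both as admissions, and the TCM criterion comes from a CMS source that the SAP cites without saying how observation counts.

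A reader might also infer that these patients cannot have the event. That is too strong: the event is a billed code, so a code billed for one of them would count.

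**Conclusion.** The inconsistency is real on the SAP's own wording: eligibility in 4.5 depends on an inpatient stay, and the denominator in 5.1 and 6.2 does not. ED-to-home patients are the clear case. Observation patients are an open question.

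The direction is known in part. Billing rates are understated. With equal shares the odds ratio moves toward 1, by about 8% to 22% at a 30% share under the three assumed pairs of rates above, and by less at smaller shares. With unequal shares it can move either way. The actual size is unknown, since the ineligible share, the billing rates and any imbalance are all assumed. The documents do not support a claim that the planned comparison is biased by a stated amount.

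This concerns one secondary process endpoint in one payer stratum. It should be corrected because the fix is cheap and the endpoint is hard to interpret without it. A neighbouring gap needs its own sentence: 4.5 calls patients who die or are readmitted within 30 days ineligible, and 6.2 does not say how they enter the TCM denominator. Those events follow discharge, so excluding on them would need separate justification.

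**What to change.** In SAP 4.5 and 6.2:

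1. Define a TCM-eligible analysis set: FFS Medicare patients with 30 days of continuous coverage whose index stay was TCM-eligible, excluding ED-to-home index visits. Use item 26 of the enrolment form, confirmed by the linked index claim, with the same rule in both arms and both phases.
2. State how index observation stays count under the cited CMS criteria, and run the analysis with and without them. SAP 4.1 already names the claim codes that identify observation stays.
3. Report the number and share excluded by arm and by phase, so that any imbalance is visible.
4. Keep the analysis of all covered FFS patients alongside, because index status arises after cluster randomisation.

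The cost is SAP wording, one filter on data already collected and one additional model run. The downsides are slightly fewer patients and an analysis set conditioned on a status determined after the hospitals were randomised. Items 3 and 4 are there to expose that.

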6.3 Analysis of Time-to-Event Endpoints

6.3.1 One-Year Mortality Analysis

Analysis of the one-year mortality endpoint will be performed using a Cox proportional hazards model that adjusts for the covariates described in Section 6.1. Analyses will be performed using the method of Wei, et al.⁵ which models the marginal distribution for event times and account for correlation between event times within a hospital unit through use of a robust sandwich variance estimator for model parameters.

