analyses. The analyses will be performed at the individual level with adjustment for lack of independence between hospitals. The primary analysis of patient-centered outcomes will occur at the end of Phase 1.

Subjects Selection Criteria

Inclusion Criteria:

 Patients aged 18 years or older, discharged home from a participating COMPASS Study hospital with a diagnosis of ischemic or hemorrhagic stroke or transient ischemic attack (TIA).

Exclusion Criteria:

- Patients transferred to another short-term acute care hospital, skilled nursing facility, inpatient rehabilitation facility, or hospice.
- Patients with a diagnosis of subdural or aneurysmal subarachnoid hemorrhage.
- Patients who speak neither English nor Spanish.

Sample Size:

- Approximately 6,000 potentially eligible participants during Phase 1
- Approximately 6,000 potentially eligible participants during Phase 2

Intervention and Interactions

As described in the Methods section above, the trial has two Phases (see Figure 1).

- Phase 1: Patient enrollment for Phase 1 of the trial will run from June 2016 to March 2018. Phase 1 includes a control arm (Control Hospital) and an intervention arm (COMPASS-Intervention Hospitals). Details of these arms and interactions are described below. Figure 2 depicts the patient flow of activities for Phase 1 when there is a control arm and COMPASS intervention arm.
- Phase 2: Patient enrollment for Phase 2 of the trial will run from November 2017 January 2019. Phase 2 includes an intervention arm (COMPASS-Intervention hospital) and the other arm is COMPASS Hospitals who will sustain the COMPASS intervention using their own hospital resources (COMPASS-Sustain hospital). Detail of these arms and interactions are described below.
- Note, that there is some overlap between Phases 1 and 2. The overlap is due to differences in the timing of hospital recruitment and enrollment (i.e. larger hospitals enrolled patients faster).

COMPASS will support hospitals in implementing structured post-acute stroke services consistent with CMS transitional care codes and management. Hospitals which participate are implementing COMPASS as the new standard of care. The goal of COMPASS is to structure and organize the processes of post-acute care to optimize patient recovery function, reduce caregiver stress, improve risk factor management, and facilitate self-management of risk factors.

Phase 1: Patients in Control Hospitals

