At 90 Days, stroke survivors will receive a phone call from the Carolina Survey Research Lab (CSRL). CSRL will follow a telephone script which includes consent (Appendix 10) and conduct blinded assessments (Appendix 23 and 24). If the patient prefers s/he can request that a proxy answer questions and provide verbal consent and HIPAA Authorization on her/his behalf. In the event contact is never made with the patient by phone or connection is lost (e.g. the number is not in service, no one answers the phone calls, call is answered but is disconnected prior to the researcher sharing the reason for calling, or there is loss of connection during the call) we will mail an abbreviated version of the survey with a letter explaining the survey purpose (Attachment 25). We will also include a self-addressed envelope with prepaid postage to the patient to gather responses via paper survey. This abbreviated survey contains the SIS-16, global health rating scale and blood pressure questions. (Note: this is identical to the Control group)

Approximately one year later the study will acquire claims data from Medicare, Medicaid, State Insurance Plan, and Blue Cross Blue Shield. We plan to use a HIPAA Waiver to acquire the data sets and along with this application we are asking for a waiver of signed consent to link all enrolled patients to the claims data sets. (Note: this is identical to the Control group).

Phase 2: COMPASS-Intervention & COMPASS-Sustain Hospitals

Hospitals which were randomized to the control-arm in Phase 1 of the study will be encouraged to cross over to provide the COMPASS Intervention during Phase 2 of the study. Hospitals that were randomized to the COMPASS Intervention-arm during Phase 1 of the study will be encouraged to continue providing all of the COMPASS Intervention to eligible patients (Sustain Sites). Both the Intervention and the Sustain Sites will provide the same intervention as described in this section. This intervention is nearly identical to the Phase 1 Intervention. Minor changes were made in order to streamline some of the intervention activities based on lessons-learned from Phase 1. The structure, however, remains unchanged: Patients who enter the study through a participating hospital will receive: (1) a follow-up phone call 2 days after being discharged from the hospital, (2) a 7-14 day Advanced Practice Provider visit, (3) a follow-up 30 day phone call, and (4) a follow-up 60 day phone call.

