5.2 Phase 2 Intent-to-Treat Analyses

We will perform intent-to-treat analyses comparing outcomes in Phase 2 to Phase 1 with respect to all endpoints listed in Table 1 stratified by insurance provider as described in Section 5.1. Phase 2 analyses will include an analysis of Sustainability that compares Phase 2 Sustainability to the Phase 1 Intervention phase. The analysis populations will be defined as above in Section 5.1 with the added requirement that the analysis is restricted to hospitals that were randomized to INV in Phase 1 and that delivered the COMPASS intervention per protocol to at least 1 participant in Phase 2 Sustainability. Phase 2 analyses will also include an analysis of pre-post comparative effectiveness that compares Phase 2 Intervention to Phase 1 Usual Care. This analysis is restricted to the set of hospitals that were randomized to Usual Care in Phase 1 and that delivered the COMPASS intervention to Phase 1 Usual Care in Phase 2.

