6.1 Covariate Adjustment

Unless otherwise stated below, where feasible the following covariates will be incorporated in analysis models for all endpoints described in Table 1.

- 1. Study Arm (intervention, usual care) ITT Phase 1 analyses only
- 2. Study Phase (sustainability, intervention) ITT Phase 2 sustainability analyses only
- 3. Study Phase (intervention, usual care) ITT Phase 2 effectiveness analyses only
- 4. Race (non-white; white)
- 5. Age (degree two polynomial)
- 6. Index hospitalization diagnosis (stroke; TIA)
- 7. NIH Stroke Scale (NIHSS) Score category (0, 1-4, 5-15, and 16-42) categories may be collapsed to 5-42 due to sample size requirements.
- 8. Sex (female; male)
- 9. Prior stroke
- 10. Prior TIA

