6.3.2 Time-to-First Occurrence Endpoints

The methodology in this section pertains to the following endpoints:

- 1. Time-to-SNF or IRF admission
- 2. Continuity of care
- 3. Time to ED visit

Analysis of these time-to-event endpoints will focus on estimation of the cause-specific hazard and thus will censor patients who die at the time of their death. Such an approach is suggested by

Austin, Lee, and Fine (2016) when the focus of the analysis is addressing etiologic questions and not prediction of individual patient prognoses.⁶ The method of Wei, et al. will be used as described in Section 6.3.1. We will also censor patients without continuous insurance coverage at the time of their first break in coverage. For Phase 2, participants who have not had one year of follow-up for claims are administratively censored at the last date for which claims were available, June 30, 2019.

When only a small number of patients experience death prior to observing the time-to-event endpoint of interest, the estimated covariate effects on the cause specific hazard will be highly similar to the estimated covariate effects on the subdistribution hazard associated with the time-to-event endpoint of interest that takes into accounting death as competing risk (using the Fine-Gray model).⁷ If more than 10% of patients experience death during the one-year follow-up period prior to observing the time-to-event endpoint of interest, we will supplement estimation of covariate effects on the cause specific hazard by estimating covariate effects on the subdistribution hazard using the Fine-Gray model. As noted in Section 6.3.1, correlation between event times with a hospital unit will be accounted for through use of a robust sandwich variance estimator for model parameters.

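### The Phase 2 time-to-event models have no hospital term beyond the variance, so a risk-related change in hospital mix between phases could bias the phase hazard ratio

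*SAP*

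**What the plan says.** SAP 5.2 defines two Phase 2 comparisons, each run by payer. The pre-post analysis is "restricted to the set of hospitals that were randomized to Usual Care in Phase 1" and compares Phase 2 intervention with Phase 1 usual care. The sustainability population carries this limit: "restricted to hospitals that were randomized to INV in Phase 1 and that delivered the COMPASS intervention per protocol to at least 1 participant".

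SAP 6.1 lists the model covariates: a phase term (for pre-post, "Study Phase (intervention, usual care) ITT Phase 2 effectiveness analyses only"), race, age, index diagnosis, NIHSS, sex, prior stroke and prior TIA. It lists no hospital, volume or stroke-center term.

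The treatment of hospital differs by endpoint type:
- Binary endpoints (6.2): a hospital random effect in the model.
- Mortality (6.3.1): a marginal Cox model whose only use of hospital is to "account for correlation between event times within a hospital unit through use of a robust sandwich variance estimator for model parameters".
- SNF/IRF admission, continuity of care and ED visit (6.3.2): "The method of Wei, et al. will be used as described in Section 6.3.1".
- All-cause readmission and recurrent stroke (6.3.3): a PWP model with the same sandwich. Its risk sets are defined by event number, not by hospital.

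No separate Phase 2 model is given. The protocol's Analytical Plan makes the randomization stratum a stratification factor in the Cox mortality model. SAP 6.1 and 6.3 do not carry this over.

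**The concern.** In Phase 1, randomization of hospitals protects the marginal Cox model. In Phase 2 each hospital set is simply seen before and after, so the protection against hospital differences has to come from comparing a hospital with itself. A pooled model with a clustered variance does not do that: it also compares patients of one hospital in Phase 1 with patients of another in Phase 2.

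Suppose hospitals with higher residual risk supply a smaller share of Phase 2 patients or follow-up. The phase hazard ratio then drifts below 1 although nothing changed in any hospital, and this could be read as benefit after crossover or as a sustained effect. The opposite pattern could hide a real effect. A larger sample does not remove the drift, because it lies in the estimate and not in its variance.

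**Working it through.** The documents give no event count, power or hazard ratio for the Phase 2 claims analyses, so there is no planned figure to reproduce. They also give no per-hospital volumes by phase and no between-hospital variance. Those inputs are assumed below, and the results are ranges, not estimates for this trial.

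**1. Formula.** Let hospital *h* have residual log hazard *u* (SD σ across hospitals) and Phase 2 to Phase 1 volume ratio *f*, with correlation ρ between *f* and *u*. With a true hazard ratio of 1 in every hospital and uncommon events,

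pooled HR ≈ 1 + Cov(*f*, e^*u*) / [mean(*f*) × mean(e^*u*)] ≈ exp(ρ × σ × CV(*f*)).

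The bias is zero if ρ = 0, if σ = 0, or if *f* is the same in all hospitals.

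**2. Numbers for σ = 0.25**, with *f* uniform over the stated range:

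| Range of *f* | Mean, SD, CV | ρ = -0.3 | ρ = -0.5 |
|---|---|---|---|
| 0-100% | 0.5, 0.289, 0.577 | exp(-0.043) = 0.96 | exp(-0.072) = 0.93 |
| 50-100% | 0.75, 0.144, 0.192 | exp(-0.014) = 0.99 | exp(-0.024) = 0.98 |
| 70-130% | 1.0, 0.173, 0.173 | exp(-0.013) = 0.99 | exp(-0.022) = 0.98 |

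Simulation (16 hospitals, 0.5 events per patient-year, no covariates) gave the same values to two decimals. For 0-100% it gave 0.97 to 0.96 at σ = 0.15 and 0.95 to 0.91 at σ = 0.35. A within-hospital estimate averaged 1.00 in all the 0-100% cases. At ρ = 0 and σ = 0.25 there was no bias, but the SD of the pooled log HR was 0.078 against 0.067 within hospital.

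**3. Two-group check.** If high-hazard hospitals have hazard *r* times the others and their share moves from p1 to p2, the spurious HR is (p2·*r* + 1 - p2)/(p1·*r* + 1 - p1). For *r* = 1.5:
- 50% to 40%: 1.20/1.25 = 0.96.
- 50% to 30%: 1.15/1.25 = 0.92.

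**4. Cox models with the clustered sandwich.** Assumed: 20 hospitals, 1,200 patients per phase, 35% one-year event rate, true HR 1, 600 runs. Rejection is at nominal 5%. The mix change is given as the SD of the log change in hospital weight.

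| Hospital SD | Mix change | Pooled HR, rejection | Stratified HR, rejection |
|---|---|---|---|
| 0.2 | none | 1.00, 7.2% | 1.00, 7.0% |
| 0.2 | SD 1.0, unrelated to risk | 1.00, 11.7% | 1.00, 8.0% |
| 0.2 | SD 0.5, correlation 0.5 | 1.04, 12.0% | 1.00, 7.0% |
| 0.2 | SD 1.0, correlation 0.5 | 1.09, 26.0% | 1.00, 7.8% |
| 0.4 | none | 1.00, 7.8% | 1.00, 6.2% |
| 0.4 | SD 1.0, unrelated to risk | 1.00, 13.0% | 1.00, 8.7% |
| 0.4 | SD 0.5, correlation 0.5 | 1.09, 23.7% | 1.00, 9.3% |
| 0.4 | SD 1.0, correlation 0.5 | 1.18, 38.3% | 1.00, 8.8% |

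These mix changes are large: log SDs of 0.5 and 1.0 mean CV(*f*) of √(e^0.25 - 1) = 0.53 and √(e - 1) = 1.31. They show the mechanism and that stratification removes it, not the size to expect. The positive sign follows from the assumed positive correlation.

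**5. Follow-up cut-off.** SAP 6.3.2 censors Phase 2 patients at June 30, 2019, the last date with claims. Taking Phase 2 enrollment as November 1, 2017 to January 31, 2019 (457 days), only discharges up to June 30, 2018 (242 days, 53%) can have a full claims year. Late follow-up can therefore weight hospitals that changed phase early. Mortality is not affected: SAP 3.2 links state death data for 2016-2020, and one year after the last enrollment ends in January 2020.

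**The case against.** The strongest reply is that nothing shows the hospital mix will change. This is correct, and three stronger readings fail with it.

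- A reader might infer that the mix must shift because "larger hospitals enrolled patients faster". That sentence explains why the phases overlap in time. It says nothing about a hospital's share in one phase against the other, and the protocol expects about 6,000 potentially eligible patients in each phase. That hospitals "will be encouraged to cross over to provide the COMPASS Intervention during Phase 2 of the study" makes uneven continuation possible but does not show it.
- A reader might infer that a sustainability hospital can enter with all its Phase 1 patients and a single Phase 2 patient. The rule is a threshold of per-protocol delivery to one participant, not a patient count. The analysis is intent-to-treat, so such a hospital may have many Phase 2 patients. Using the same hospitals in both phases also removes the largest mix change, which is hospital drop-out.
- A reader might extend the June 2019 cut-off to mortality. The death linkage rules that out.

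It is also fair that the size depends on the assumed volume range, that the simulations omit the 6.1 covariates (which would absorb some hospital difference), and that Phase 2 aims are exploratory in the protocol. For mortality, at an assumed 0.06 deaths per patient-year, the chance SD of the log HR was about 0.19 in the 16-hospital design, well above any shift in the table in step 2.

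Two mitigations are partial. The protocol's stratum factor covers volume and stroke-center status for mortality only, is absent from the SAP, and a stratum is not a hospital. The rural/urban hospital indicator in SAP 6.1.1 enters only sensitivity models and is subject to selection. The parent Phase 1 SAP was not available, but this addendum specifies its own time-to-event models.

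What remains is that the specification does not protect the Phase 2 estimate if the mix does shift.

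**Conclusion.** The point holds conditionally. For all six time-to-event endpoints hospital enters only the variance, so in these non-randomized before-after contrasts the phase hazard ratio can be biased. Two things are needed: hospitals' shares of patients or follow-up differ between phases, and the difference is related to hospital risk left after the 6.1 covariates. If it is unrelated to risk, there is no average bias, only a more variable estimate.

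Under the assumptions in step 2, the spurious hazard ratio ranges from about 0.93 with very uneven continuation to about 0.99 with moderate variation. A risk-mix correlation of the opposite sign would put it above 1. The cut-off is a possible driver for the claims-based endpoints only. The documents do not support saying that the Phase 2 results are biased. They support saying that the plan leaves an avoidable route to bias open. The binary endpoints, which carry a hospital random effect, are outside this point.

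**What to change.** - In SAP 6.3.1 to 6.3.3, state that the Phase 2 Cox and PWP models are stratified by hospital, with the hospital-level sandwich kept. Any supplementary Fine-Gray model needs a matching rule.
- Where payer groups or PWP event-number strata are too sparse, use hospital fixed effects or a shared frailty instead, and state the rule for switching in advance. A frailty removes most, but not all, of the between-hospital comparison.
- Tabulate patients and events by hospital and phase within payer. Report hospitals with patients in only one phase, since they drop out of the stratified estimate.
- Keep the unstratified model as a sensitivity analysis.
- Reconcile the protocol's stratum factor in the Cox mortality model with SAP 6.1 and 6.3.

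The cost is a short SAP text, a stratification term in the code and one table. Some precision is lost, mainly in the Medicaid and BCBS groups, which are likely the smaller ones. Calendar-time trends between phases are not addressed and remain a separate limitation.
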